1.1 Brief Summary

Physical fitness training improves the physical fitness level of dancers and increases their explosive power(Angioi et al., 2012; de la Cruz-Torres et al., 2019; Dowse et al., 2020; Hutt & Redding, 2014; Karim et al., 2019; Kim et al., 2017; Ko et al., 2020; Kolokythas et al., 2022; Koutedakis et al., 2007; Koutedakis & Sharp, 2004; Liu & Wang, 2024; Marshall & Wyon, 2012). In the past, traditional training methods were generally used to improve the strength of dancers, but there are drawbacks to this training method, which cannot fully develop physical fitness and may lead to athletic injuries or limitations in improving skills(Moro et al., 2020). Plyometric training is a high-intensity training method that has been shown to have significant benefits in terms of increasing explosive power (Huang et al., 2023; Ramírez-Campillo et al., 2014; Ramírez-Campillo et al., 2013). However, there is little research on the effects of plyometric training on explosive power and skill in dance programs. Exercise improves physical fitness, plyometric training improves explosive power, and plyometric training should also improve explosive power and specialized performance in Latin dancers. Therefore, the research on improving the explosive power of Latin dancers' lower limbs through plyometric training is of great theoretical and practical significance, which can find suitable means of explosive power training for Latin dance programs, provide reference for coaches in training, and increase the theoretical research on the effect of plyometric training on explosive power.

1.2 Detailed Description

The Intervention Protocol of this research used part of the research protocol of Chinese scholar Du Min (Du, 2020). This research utilized augmentative training as an intervention, with the dependent variables being the subject's lower limb explosive power and Latin dance skill performance. Through extensive literature review, countermovement jumps, standing long jump, and 20m-sprint were identified as measures of lower limb explosive power(Chen et al., 2023). The experimental and control groups will be tested on the same Cha Cha Dance Gold Medal solo routine and recorded with a video camera. Score athletic performance according to 'the Latin Dance Technical Quality Elements of the World DanceSport Federation (WDSF) 2.1 Evaluation System'. Lower limb explosive power is closely related to the skill performance of cha-cha dance, and the review of the relevant literature was

determined to be posture, balance, footwork, preparation-movement-reduction, spinning and rotation, dynamic performance, and line extension as the test indicators of elementary skill (pei, 2023). In order to make the experiment more rigorous and scientific , to reduce the interference of uncontrollable factors , this research is Cluster Randomized Controlled Trial (CRCT) design , the students come from different areas . This experiment lasted for 8 weeks, 1.5 hours each time (Du, 2020), including one hour of physical fitness training and half an hour of specialized technical training. The sample was a population of university students who had been studying Latin dance for one year as well as more than one year, from Guangxi Normal University (Guilin) and Guilin University of Electronic Technology (Beihai), a total of 48 people. Dancers were randomly assigned to two different training locations and divided into experimental and control groups. Both groups will be trained in the Cha Cha Dance Single Gold Medal Moves. The experimental group will undergo plyometric training and the control group will undergo general training. This study measured the dependent variable three times throughout the intervention: baseline before the experimental intervention, post-test 1 after 4 weeks, and post-test 2 after 8 weeks. Finally, statistical analysis was conducted on the three test results.

2 Protocol Design

The experiment will last a total of 8 weeks in order to familiarize the experimenter with the plyometric training protocol and to make the whole process more fluid. It is necessary to ensure correct technique during the jumping exercises to minimize the occurrence of injuries. This research will monitor heart rate to ensure that the training load is the same for the experimental group (plyometric training) and the control group (general training). Both groups will have the same heart rate for each session of training load from the preparation phase - training phase - stretching and relaxation phase during the intervention. The experimental and control groups will undergo 3 interventions a week, with one session lasting 90 minutes. The experimental group will perform 15 minutes of dynamic stretching, 30 minutes of Latin dance-specific technique training, 30 minutes of plyometric training, and 15 minutes of relaxation stretching. The control group will perform 15 minutes of dynamic stretching, 30 minutes of Latin dance-specific technique training, 30 minutes of general training, and 15 minutes of relaxation stretching.

Table 1 Training Intervention Information

Week	Frequency	Types	Duration (min)	Warm -up /min	Physical training /min	Specialized Training	Cool-down /min	Intensity	Suggestions
1-3	3times/week	Plyometric Training	90min	15min	30min	30min	15	(40%-50%) HRmax	
		General Training						(60%-70%) HRmax	
4-5	3times/week	Plyometric Training	90min	15min	30min	30min	15	(60%-70%) HRmax	
		Standard Training						(60%-70%) HRmax	
6-8	3times/week	Plyometric Training	90min	15min	30min	30min	15	(80%-90%) HRmax	
		Standard Training						(70%-85%) HRmax	

Table 2 Plyometric Training Protocol for Experimental Group

Week	Movements	Sets/reps	Rest (sets/reps)	Intensity	Warm up	Cool down
1-3	Standing Vertical Jump	10sets / 3reps	60-120s	(40%-50%) HRmax	Move the wrist, shoulder, hip, knee, and ankle.	Muscle stretching—arm cross stretch, low lunge stretch, half split, ankle to knee
	Consecutive leapfrog	8sets / 2reps				
	Squat jump	6sets / 3reps				
	Rocket jump	6sets / 3reps				
	High knee	10sets / 3reps				
	Jumping jacks followed by lateral quick run	10sets / 2reps				
4-5	Jump on the jump box	10sets / 3reps	60-120s	(60%-70%) HRmax	Move the wrist, shoulder, hip, knee, and ankle.	Muscle stretching—arm cross stretch, low lunge stretch, half split, ankle to knee
	Frontal consecutive jumping obstacle	8sets / 3reps				
	Rocket jump	10sets / 3reps				
	Star jump	6sets / 3reps				
	Squat jump	10sets / 3reps				
	Consecutive leapfrog	6sets / 3reps				
6-8	Tuck jump	10sets / 3reps	60-120s	(80%-90%) HRmax	Move the wrist, shoulder, hip, knee, and ankle.	Muscle stretching—arm cross stretch, low lunge stretch, half split, ankle to knee
	Weighted leapfrog followed by vertical jump	10sets / 3reps				
	Jump on the jump box	10sets / 3reps				
	Depth jump followed by jump on the jump box	8sets / 3reps				
	Depth jump over obstacle	10sets / 3reps				
	Side lunge	10sets / 3reps				

Table 3 General Training Protocol for Control Group

Week	Movements	Sets/reps	Rest (sets/reps)	Intensity	Warm up	Cool down
1-3	Jumping Jacks	15sets / 3reps	60-120s	(60%-70%) HRmax	Move the wrist, shoulder, hip, knee, and ankle.	Muscle stretching—arm cross stretch, low lunge stretch, half split, ankle to knee
	Split-legged left-right jump	10sets / 3reps				
	50%1RM squat	10sets / 3reps				
	Single-leg squat	10sets / 3reps				
	Supine leg raise	10sets / 3reps				
	Horizontal skip	10sets / 3reps				
4-5	20%1RM Calf raises	10sets / 3reps	60-120s	(60%-70%) HRmax	Move the wrist, shoulder, hip, knee, and ankle.	Muscle stretching—arm cross stretch, low lunge stretch, half split, ankle to knee
	60%1RM Squat	10sets / 3reps				
	50%1RM Deadlift	10sets / 3reps				
	Split-legged left-right jump	10sets / 3reps				
	Horizontal skip	10sets / 3reps				
	Lunge squat	10sets / 3reps				
6-8	30%1RM Calf raises	10sets / 3reps	60-120s	(70%-85%) HRmax	Move the wrist, shoulder, hip, knee, and ankle.	Muscle stretching—arm cross stretch, low lunge stretch, half split, ankle to knee
	60%1RM squat	10sets / 3reps				
	50%1RM Deadlift	10sets / 3reps				
	Lunge squat	10sets / 3reps				
	Standing leg lift	15sets / 3reps				
	Prone sprint	30sets / 3reps				

3 Questionnaire information

The questionnaire adopts a 4-point ordinal scale to evaluate intervention, with 1- 4 representing increasing support (1=not relevant, 2=somewhat relevant, 3=quite relevant, 4=highly relevant). Please score the plyometric training intervention. If there are other content, you can add them and indicate the name. After reading the questionnaire, please rate the following aspects and tick "√"on the corresponding rating scale.

Table 4 Expert Evaluation Form

4 Outcome Measures

4.1 Lower limb explosive power:

[figure not shown]
Countermovement jumps: experimenters test using either arm swing or crossed hips (without any arm swing) while performing vertical longitudinal jumps on a smart jumping mat. The experimenter in this research uses a cross-legged waist when performing both the pre-test and post-test. The Smart Jump Pad in this research has been performed to measure the performance of the CMJ by providing signals from the platform in an iPad 7,5 IOS 12.1.1). When the test equipment is ready, under the direction of the test administrator, the experimenter stands on the Smart Jump Mat and performs a vertical longitudinal jump. The experimenter jumps to the best of their ability and each jump was automatically recorded on the iPad. Each participant jumped three times, and the best jump results are selected for data analysis in this research.(Meszler et al., 2019)

.

Standing long jumps: Measure the distance of the standing long jump with a measuring tape.

Participants stand slightly apart in front of the jump line, bend their knees, and move their arms backwards, then swing their arms and jump as far as possible; Stand on both feet while maintaining an upright position; Conduct two tests. Record the best score from two tests with an accuracy of 1 centimeter (Ambrozy et al., 2022).

20m-sprint : Use a stopwatch to record the duration of the participants' 30 m sprint.

Set cones at 0 and 20 meters along a straight line. Participants place their toes on the starting line or behind the starting line, start from a stationary position, and sprint at maximum speed over the cone at a distance of 20 meters before safely slowing down (Fischetti et al., 2018).

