4.2 Latin Dance Performance

Using a video camera, a recorded video of the Cha Cha Gold Medal solo routine is send to the 6 judges, and the pre- and post-tests need to be rated using the same criteria 'the Latin Dance Technical Quality Elements of WDSF2.1 Evaluation System' Objectively assess posture, balance, footwork, preparation-movement-reduction, spinning and rotation, dynamic performance, and line extension (pei, 2023).

Table 5 Scoring Standards for the Qualities of Cha-cha-cha Dancing Skills

Indictors	Very excellent. (10 points)	excellent (8 points)	Above average (6 points)
Posture	Requires the ability to adopt and maintain correct posture during dynamic movement and, with minimal effort, to consciously demonstrate spatial transition postures.	It can drive the entire body to be integrated into the pose, so that the gesture blends with the posture.	The body, in static or dynamic motion, has a well-balanced body structure that includes the head, shoulders, chest, hips, legs, and feet.
Balance	Static: the line of gravity can be reconstructed after dynamic balance movement; Dynamic: can be used naturally and smoothly to generate three-dimensional movement effects, to realize the balance and effect of dance.	Static: can keep its own gravity in the extension line; Dynamic: the use of correct force to achieve dance balance, producing three-dimensional effects	Static: maintains the line of gravity from head to toe; Dynamic: maintaining balance while moving.
Footwork	Control of the spine through the flow of the steps and the transition between centers of gravity to complete the footwork.	Ability to properly utilize foot technique, connecting the necessary foot pressures and hip and body movements.	Ability to properly utilize foot technique.
Preparation-movement-reduction	The ability to perform the full range of motion with a natural and smooth transition from one movement to the next.	It is possible to make the transition from one movement to another during the performance of a complete movement.	Most of the articulated pre-reduction from movement to movement can be accomplished when performing full movements.
Spinning and rotation	Maximize the use of centripetal and centrifugal forces in rotating and turning motions.	It is possible to combine the sagittal plane with the coronal plane when accomplishing rotational and turning movements.	Ability to combine the sagittal and coronal planes most of the time when completing rotational and turning maneuvers

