Dynamic performance	Precise use and maximization of power generation in dance movements.	Precise use of power in dance movements	Precise application of power in most dance movements
Line extension	Maintains the lines and extensions of all body parts in both static and dynamic situations.	Maintains most body lines and extensions in both static and dynamic situations.	Maintains a portion of the body line and extends the line in both static and dynamic situations.

Table 6 Outcome Measurement Information

Test Name	Outcome Measure	Measure Method	Instrument	Unit	Suggestions
Explosive power	Countermovement jumps	Recorded maximum altitude	Smart jump mats, iPad	Centimeters (cm)	
	Standing long jumps	Measure the distance of the standing long jump with a measuring tape.	Measuring tape	Centimeters (cm)	
	20m-sprint	Use a stopwatch to record the duration of the participants' 20 m sprint.	Stopwatch	Seconds	
Posture	6 Experts	Recording cha-cha-cha solo gold medal moves, expert scoring	M120 high-speed camera	scores	
Balance	6 Experts	Recording cha-cha-cha solo gold medal moves, expert scoring	M120 high-speed camera	scores	
Footwork	6 Experts	Recording cha-cha-cha solo gold medal moves, expert scoring	M120 high-speed camera	scores	
Preparation-movement-reduction	6 Experts	Recording cha-cha-cha solo gold medal moves, expert scoring	M120 high-speed camera	scores	
Spinning and rotation	6 Experts	Recording cha-cha-cha solo gold medal moves, expert scoring	M120 high-speed camera	scores	
Dynamic performance	6 Experts	Recording cha-cha-cha solo gold medal moves, expert scoring	M120 high-speed camera	scores	
Line extension	6 Experts	Recording cha-cha-cha solo gold medal moves, expert scoring	M120 high-speed camera	scores	

5 Questionnaire information

This questionnaire adopts a 5-point Likert scale, with 1-5 representing increasing support (1=strongly disagree; 2=disagree; 3=not necessarily; 4=agree; 5=strongly agree). Please score the intervention program. If there is other content, you can add them and indicate the name. After reading the questionnaire, please rate the following aspects and tick "√" on the corresponding rating scale.

Table 7 Expert Evaluation Form for Outcome Measurement

6 References

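### Section 1.2 labels the trial cluster-randomised but describes dancers being assigned; on both readings that need no unmentioned grouping, the training effect cannot be separated from location

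*Protocol*

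**What the plan says.** The allocation is described only in section 1.2 (Detailed Description) of the protocol. Three statements matter.

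- Design label: "this research is Cluster Randomized Controlled Trial (CRCT) design , the students come from different areas". The only remark attached to it is that students come from different areas.
- Allocation: "Dancers were randomly assigned to two different training locations and divided into experimental and control groups". Here the dancer is the thing assigned.
- Source of the sample: "from Guangxi Normal University (Guilin) and Guilin University of Electronic Technology (Beihai), a total of 48 people".

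No section defines the cluster, gives the number of clusters per arm, or says which arm trains at which location or university. The same section plans repeated measurement: "This study measured the dependent variable three times throughout the intervention: baseline before the experimental intervention", followed by tests after 4 and 8 weeks.

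**The concern.** The label makes a group the randomised unit, while the allocation sentence makes it the dancer. Both cannot be right. The unit of randomisation and the number of units are facts of the design, so this is not a detail that a protocol may leave to its SAP.

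The trial's central conclusion is at stake, namely that plyometric training does better than general training. If each arm has its own location, everything that differs between the two places over 8 weeks (trainer, facilities, group effects, concurrent activity) is part of the arm contrast. Whether a p-value from the 48 dancers tests training, tests training plus location, or has no support from the randomisation depends on a fact that the protocol states in two incompatible ways.

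**Working it through.** The protocol gives no sample-size calculation or error rate for this point, so there is no figure to reproduce.

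**Inputs from section 1.2:** 2 arms, 2 universities, 2 locations, 48 dancers.

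**Reading A: universities or locations were randomised, one per arm.** Let k be the number of clusters per arm, so k = 1.

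- Between-cluster degrees of freedom = 2k − 2 = 0.
- Possible allocations = C(2k, k) = C(2, 1) = 2. Smallest two-sided randomisation p = 2/C(2k, k) = 2/2 = 1.0.

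This count needs no intracluster correlation (ICC). The randomisation alone supports no test. A dancer-level test needs a further assumption about location.

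**Reading B: dancers were randomised individually, one location per arm.** With an assumed 24:24 split there are C(48, 24), about 3.2 × 10^13, allocations, so the count is no obstacle. The test is valid for the package that was assigned, training plus location. Training and location change together for every dancer, so the data cannot divide the effect between them.

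**Reading C: dancers were randomised individually, both programmes at both locations.** Location is then not tied to arm, and only the label is wrong. Section 1.2 does not say that this is the arrangement.

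**Illustrations only.** The protocol gives no ICC, correlation, location effect, group split or test. All are assumed here: 24 per arm and a two-sided 5% t-test on 46 df (critical value 2.013).

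*Reading A, change from baseline.* Let r be the within-location correlation of baseline and post-test, and c the correlation of the location effect between the two times. The true variance of the arm difference exceeds the naive variance by the factor

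F = 1 + 24 × ICC × (1 − c) / [(1 − ICC)(1 − r)],

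and type I error = 2 × P(t46 > 2.013/√F). Example with ICC 0.05, r 0.8, c 0.8: F = 1 + 0.24/0.19 = 2.263, √F = 1.504, 2.013/1.504 = 1.338, type I error 18.7%.

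| ICC (r = 0.8) | c = 1.0 | c = 0.9 | c = 0.8 | c = 0.5 |
|---|---|---|---|---|
| 0.01 | 5.0% | 6.4% | 7.7% | 11.9% |
| 0.05 | 5.0% | 12.2% | 18.7% | 32.9% |
| 0.10 | 5.0% | 19.4% | 29.9% | 47.1% |

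Baseline-adjusted ANCOVA, simulated at ICC 0.05, gives 6.5%, 12.3%, 17.9% and 30.7% across the same columns. The change score holds its level exactly when location differences are constant over time (c = 1.0). Both analyses lose it as those differences drift.

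*Reading B, no training effect.* With a location effect of δ SD, the noncentrality is δ√(24/2) = δ√12. For δ = 0.2, 0.3 and 0.5, p < 0.05 occurs in about 10%, 17% and 40% of trials. These are correct detections of the package that would be wrong if credited to training.

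**The case against.** **One cluster per arm is never stated.** This stands. The only allocation sentence names dancers, so reading B is at least as natural as reading A, and under reading C a label is all that needs correcting. A reader might infer from the design label that the trial is certainly a two-cluster trial; the document does not establish that. What it does establish is the conflict between label and allocation sentence.

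**Even under reading A, a test may be possible.** This also stands. A reader might infer that no analysis could ever give a valid between-group test. That goes too far: the protocol plans a baseline, and a change-score test keeps its 5% level if location differences are constant over time. The limit is narrower. Such a test rests on an assumption that two clusters cannot check, not on the randomisation.

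**Smaller units, such as classes, may have been randomised.** A reader might infer this to rescue the label, but no section mentions such units. Stating the unit and the number per arm would settle it.

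**Separate locations may be deliberate.** Section 1.2 gives less interference from uncontrolled factors as the reason for the design. Under reading B that is a defensible choice. It limits what may be concluded but does not invalidate the comparison.

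**Conduct and measurement limit location effects.** In part they do. Section 2 gives both arms the same schedule ("The experimental and control groups will undergo 3 interventions a week, with one session lasting 90 minutes"). In section 4.1, for the countermovement jump, "each jump was automatically recorded on the iPad". In section 4.2 "a recorded video of the Cha Cha Gold Medal solo routine is send to the 6 judges". These features do not remove differences between locations that develop over 8 weeks of training, and the sprint is timed by hand (Table 6: "Use a stopwatch to record the duration of the participants' 20 m sprint").

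**Conclusion.** The point holds, and the text must be corrected before a conclusion about training is drawn. It is certain that the design label and the allocation sentence conflict and that the unit of randomisation, the units per arm and the location of each arm are not fixed.

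The consequence is conditional. With one university or location randomised per arm, there are 0 between-cluster degrees of freedom and the smallest randomisation p is 1.0, so any dancer-level p-value depends on an uncheckable assumption about location. With dancers randomised and one location per arm, the p-value is valid for training plus location only. With both programmes at both locations, only the label is wrong. The first two readings need no grouping or arrangement beyond those that section 1.2 names, and in both the training effect cannot be separated from location.

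The degrees of freedom and minimum p follow from the count of clusters alone. The error rates of 5.0% to 47.1% and the 10%, 17% and 40% figures rest wholly on assumed values. They show direction and possible size and are not estimates for this trial.

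**What to change.** In section 1.2, reconcile the two sentences by stating one unit of randomisation, the number of units per arm, and which arm trains at which location. Then apply the matching wording.

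- **One university or location randomised per arm:** describe the design as allocation of one cluster per arm. State that dancer-level p-values rest on an uncheckable assumption of no location-by-time difference. Report the group comparison as descriptive, without a claim of efficacy.
- **Dancers randomised, one location per arm:** replace the cluster label with *individually randomised*. State that arm is confounded with location, and do not attribute the difference to plyometric training alone.
- **Dancers randomised, both programmes at both locations:** correct the label and state the arrangement. Nothing more is needed.

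The change is wording only and needs no extra dancers or sessions. Its cost is a weaker stated conclusion in the first two cases.

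### Section 2 promises the same heart rate in both groups at every session, but Tables 1-3 prescribe non-overlapping intensities in weeks 1-3 (40-50% against 60-70% HRmax)

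*Protocol*

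**What the plan says.** Section 2 (Protocol Design) makes the claim in two consecutive sentences. The first gives the purpose of monitoring: "This research will monitor heart rate to ensure that the training load is the same for the experimental group (plyometric training) and the control group". The second gives the result to be achieved: "Both groups will have the same heart rate for each session of training load from the preparation phase", and it continues: "training phase - stretching and relaxation phase during the intervention". It applies to each session and names the training phase.

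The tables that follow set the intensity by block of weeks. Table 1 gives both arms, Table 2 repeats the plyometric values and Table 3 the control values:

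| Weeks | Plyometric (Tables 1, 2) | Control (Tables 1, 3) |
|---|---|---|
| 1-3 | 40-50% HRmax | 60-70% HRmax |
| 4-5 | 60-70% HRmax | 60-70% HRmax |
| 6-8 | 80-90% HRmax | 70-85% HRmax |

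On frequency, section 2 says: "The experimental and control groups will undergo 3 interventions a week, with one session lasting 90 minutes". Section 1.2 sets the tests at "baseline before the experimental intervention, post-test 1 after 4 weeks, and post-test 2 after 8 weeks".

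**The concern.** The text and the tables cannot both be followed in weeks 1-3. Each band appears in two tables that agree, so a slip in a single cell is an unlikely explanation. Nothing else in the protocol reconciles the two or limits the equality statement to certain weeks or phases.

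Equal load by heart rate is the only control of training intensity between the arms that the protocol states. A report that repeated the section 2 sentences would tell readers that load was matched, although most sessions before the first follow-up test were prescribed at different intensities. What is at stake is the meaning of a between-group difference, above all at post-test 1: it compares two programmes, not two modes of training at equal load.

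**Working it through.** The protocol gives no figure to reproduce. The check compares the two arms' bands block by block and counts sessions.

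**Sessions.** At 3 per week: 3 × 3 = 9 (weeks 1-3), 3 × 2 = 6 (weeks 4-5), 3 × 3 = 9 (weeks 6-8), total 24. Post-test 1 follows week 4, so 9 + 3 = 12 sessions precede it.

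**Overlap and gap by block** (control minus plyometric, in points of %HRmax; lowest = control lower edge − plyometric upper edge, highest = control upper edge − plyometric lower edge):

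| Weeks | Sessions | Shared band | Lowest gap | Highest gap |
|---|---|---|---|---|
| 1-3 | 9 | none | 60 − 50 = +10 | 70 − 40 = +30 |
| 4-5 | 6 | 60-70% | 60 − 70 = −10 | 70 − 60 = +10 |
| 6-8 | 9 | 80-85% | 70 − 90 = −20 | 85 − 80 = +5 |

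The strict contradiction covers weeks 1-3: 9/24 = 37.5% of all sessions, and 9/12 = 75% of those before post-test 1.

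**Mean prescribed gap, from band edges only:**
- Up to post-test 1: (9×10 − 3×10)/12 = +5 to (9×30 + 3×10)/12 = +25. Control is higher throughout this range, so the tables fix the sign.
- Up to post-test 2: (9×10 − 6×10 − 9×20)/24 = −6.25 to (9×30 + 6×10 + 9×5)/24 = +15.6. The sign is not fixed.

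**Mean prescribed intensity, assuming band midpoints:**
- Up to post-test 1: plyometric (45×9 + 65×3)/12 = 50; control 65; gap 15.
- All 24 sessions: plyometric (45×9 + 65×6 + 85×9)/24 = 65.0; control (65×15 + 77.5×9)/24 = 69.7; gap 4.7.

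**Could absolute heart rates match although the relative bands differ?** In weeks 1-3 this would need HRmax in the plyometric arm to be at least 0.60/0.50 = 1.2 times that in the control arm. Nothing in the protocol suggests such a difference between two groups of university students.

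**The case against.** The strongest reply is that little depends on the equality statement. The protocol's aim is to find a suitable training method, which is a comparison of programmes and needs no load matching. Section 1.1 says "Plyometric training is a high-intensity training method", so rising intensity may be part of the intervention. Equal heart rate would not isolate plyometric mode anyway: the arms also differ in exercises, listed volume and %1RM loads, and in site, since "Dancers were randomly assigned to two different training locations and divided into experimental and control groups". No listed outcome uses heart rate. This stands, and it is why the tables are not called wrong and no bias is claimed. It does not rescue the two sentences, which still state something the tables exclude.

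The scope of the bands is also unsettled. Table 1 sets intensity against the 90-minute session, Tables 2 and 3 against the listed exercises. If the bands cover only the 30-minute physical block, the conflict concerns one third of each affected session. That is a fair limit, but this block is where the arms are meant to differ and belongs to the training phase that section 2 names.

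The averaged gaps use a summary that the protocol does not define as load. That is true; the finding needs only the non-overlap and the session counts, and the averages merely describe the prescription.

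Finally, monitoring heart rate does not mean storing it, and Table 6 does not list it as a measure. This stands, and it affects only the suggested heart-rate table.

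**Conclusion.** The concern holds. As prescribed, the arms cannot have equal heart rate relative to HRmax during the listed exercises in weeks 1-3; control is 10 to 30 points of %HRmax higher there. Weeks 6-8 are not a strict contradiction, and weeks 4-5 match. The sizes rest on three sessions a week being delivered and on the bands being followed; the bands are prescriptions, and achieved heart rates could differ from them. On the midpoint assumption the cumulative gap shrinks between the two post-tests without changing sign, but the band edges alone do not settle the sign by post-test 2. No effect on any outcome has been shown. The defect is a false statement about what the comparison holds constant. It should be fixed.

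**What to change.** - Replace the two equal-load sentences in section 2 with a statement that the programmes differ in prescribed heart-rate intensity in weeks 1-3 and 6-8.
- When the results are written up, word the conclusion as a comparison of two training programmes not matched on load.
- Report recorded heart rate by arm for weeks 1-3, 4-5 and 6-8. The protocol should say that the monitored values are stored, since the table depends on it.
- Set identical bands only if equal load is truly intended. Tables 2 and 3 tie each band to particular exercises, repetitions and rests, so these may have to change too.

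The cost is two sentences and one table, plus the work of storing heart rate if that is not already planned. The training itself need not change. The price is a narrower claim: the report can no longer say that load was equal.

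### The sets, reps and rest printed in Tables 2 and 3 do not fit the 30-minute training block in any phase of either arm; the set and rep labels may be inverted

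*Protocol*

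**What the plan says.** Section 2 (Protocol Design) sets the frequency and length: "The experimental and control groups will undergo 3 interventions a week, with one session lasting 90 minutes". For the plyometric arm it says "The experimental group will perform 15 minutes of dynamic stretching, 30 minutes of Latin dance-specific technique training, 30 minutes of plyometric training", followed by a cool-down. The control arm has the same structure, with "30 minutes of general training, and 15 minutes of relaxation stretching". Table 1 repeats 30 minutes of physical training for every phase.

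Tables 2 and 3 list six movements for each of weeks 1-3, 4-5 and 6-8. Each movement has a number of sets and a number of reps. A rest of 60-120 s is printed once per phase in a column headed "Rest (sets/reps" (closing bracket cut here). The protocol does not say whether that rest falls between sets, between reps or between movements, or whether all six movements are done in every session.

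Section 1.2 describes the 90 minutes in another way: "including one hour of physical fitness training and half an hour of specialized technical training".

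**The concern.** A list of 50 to 85 sets per session, with at least a minute of rest between sets, looks far too long for half an hour. If so, the time allotted and the programme prescribed contradict each other, in the intervention and in the comparator.

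Tables 1 to 3 are the only description in this document of what each arm does. Section 1.2 says that part of a cited master's dissertation was used, but not which part. The participants train at two locations, so staff could resolve the conflict differently: by shortening rest, dropping movements, overrunning the block or swapping the labels. A later reader could not tell which programme was compared with which.

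**Working it through.** **The plan's own session total.** 15 + 30 + 30 + 15 = 90 minutes, which agrees with the stated session length. The figure under test is the 30-minute (1,800 s) physical-training block.

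**Inputs from Tables 2 and 3, sets as printed**

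- Plyometric, weeks 1-3: 10+8+6+6+10+10 = 50
- Plyometric, weeks 4-5: 10+8+10+6+10+6 = 50
- Plyometric, weeks 6-8: 10+10+10+8+10+10 = 58
- Control, weeks 1-3: 15 + 5×10 = 65
- Control, weeks 4-5: 6×10 = 60
- Control, weeks 6-8: 4×10 + 15 + 30 = 85

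Rest is 60 to 120 s.

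**Assumptions.** All six movements are done each session, and the rest printed once per phase applies to every movement. Both are inferences from the layout. Working time is set to zero, which favours the protocol.

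**Formulas.** Rest within movements only = (sets − 6) × rest. Rest between all successive sets = (sets − 1) × rest.

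| Phase | Printed sets | Within movements, 60 s | Between all sets, 60 s | Within movements, 120 s |
|---|---|---|---|---|
| Plyometric 1-3 | 50 | 44 min | 49 min | 88 min |
| Plyometric 4-5 | 50 | 44 min | 49 min | 88 min |
| Plyometric 6-8 | 58 | 52 min | 57 min | 104 min |
| Control 1-3 | 65 | 59 min | 64 min | 118 min |
| Control 4-5 | 60 | 54 min | 59 min | 108 min |
| Control 6-8 | 85 | 79 min | 84 min | 158 min |

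The smallest entry, 44 minutes, exceeds 30 before any exercise is done. To fit with zero working time, rest could be at most 1,800/44 = 40.9 s in plyometric weeks 1-5 and 1,800/79 = 22.8 s in control weeks 6-8. Both lie below the printed minimum of 60 s.

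**Labels inverted.** In every row the second number is 2 or 3, while the first runs from 6 to 30. Read the other way round, plyometric weeks 1-3 have 3+2+3+3+3+2 = 16 sets and the other five phases have 6×3 = 18.

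- Rest within movements: 10 to 20 min (16 sets) and 12 to 24 min (18 sets) over 60-120 s.
- Rest between all sets: 15 to 30 min (16 sets) and 17 to 34 min (18 sets).

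At 120 s between all sets, no working time is left. At 120 s within movements, control weeks 6-8 leave (1,800 − 12×120)/255 = 1.4 s per repetition, where 255 = 85×3 is that phase's total. The documents give no working time per set. If 20 to 40 s is assumed, 18 sets with rest within movements allow a mean rest of (1,800 − 18×20)/12 = 120 s down to (1,800 − 18×40)/12 = 90 s. With rest between all sets they allow (1,800 − 18×20)/17 = 84.7 s down to (1,800 − 18×40)/17 = 63.5 s.

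**How far the two readings differ.** Total repetitions are identical, because sets × reps does not depend on the order. The ratio of printed to inverted sets is 50/16 = 3.1, 50/18 = 2.8 and 58/18 = 3.2 (plyometric), and 65/18 = 3.6, 60/18 = 3.3 and 85/18 = 4.7 (control).

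**The case against.** The best reply is that this is a label slip. The tables look like 3 sets of 10 written backwards, and 30 prone sprints read more naturally as repetitions than as sets. Most of this stands: inversion is the likeliest explanation and removes most of the excess. It does not close the matter. Every row of both tables prints the same order and nothing tells the reader to reverse it. Even when inverted, the upper end of the rest range fits or fails according to where the rest applies and how long a set takes.

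A second reply is that the clash depends on premises the protocol does not state. That is correct, and the point is made on those premises. Two other readings could ease it. Rest only between the six movements would take 5 gaps, or 5 to 10 minutes, but the column header refers to sets and reps. Spreading the movements over the three weekly sessions has no support in the text. A reader might infer from that reading a threefold uncertainty in weekly training volume, but the documents do not support that inference.

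A third reply is the hour of fitness training in section 1.2. It is most naturally the 15-minute warm-up, the 30-minute block and the 15-minute cool-down, and Table 1 fixes the block at 30 minutes. Even a 60-minute block would be too short for control weeks 6-8 at 60 s (79 minutes) and for every phase at 120 s (at least 88 minutes).

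**Conclusion.** The concern holds in conditional form. With all six movements each session and the printed rest between the printed sets, all six phase-by-arm combinations overrun the 30-minute block on rest alone: by at least 14 to 22 minutes in the plyometric arm (44 to 52 against 30) and 24 to 49 minutes in the control arm (54 to 79 against 30). These are lower bounds, at the shortest rest and with zero exercise time.

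A reader might go further and infer that the programme cannot be delivered at all. The documents do not support that, since inverted labels give a workable session over at least part of the rest range. Nor do they support the opposite claim that inversion settles everything: at an assumed 40 s per set, five of the six phases allow at most 90 s of rest within movements, the midpoint of the printed range.

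What is established is that the structure of both programmes is contradictory as written, with a 2.8- to 4.7-fold difference in the number of sets between the two label readings. Sample size and analysis are not affected. It should be corrected because it concerns the definition of the treatments being compared.

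**What to change.** Across section 2 and Tables 1 to 3, the sponsor should reconcile:

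- the set and rep labels;
- the scope of the rest interval (between sets, reps or movements);
- whether all listed movements are done in each session;
- the 30-minute block.

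The sponsor should then check by arithmetic, with working time included, that each phase in both arms fits the stated time over the whole stated rest range. No particular prescription is proposed here. The cost is a correction to protocol text and tables, with no extra data or participants.
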